7.2 Pathology Requirements

Stained pathology slides are not required for this protocol. Documentation of initial pathology will be performed by verifying the original pathology report.

7.3 Translational Research

7.3.1 Specimen Requirements

7.3.1.1 Blood Specimens

For detailed instructions on processing and shipping please see
Procedure Manual – Specimens SOP

7.3.1.2 Urine Specimens

For detailed instructions on processing and shipping please see
Procedure Manual – Specimens SOP

7.3.1.3 Tumor Specimens

For detailed instructions on processing and shipping please see
Procedure Manual – Specimens SOP

7.3.2 Biomarker processing and sample handling.

For detailed instructions on processing and shipping please see Procedure Manual – Specimens SOP

For any questions regarding biomarker processing, supplies and shipping, please call [contact].

7.4 Quality of Life

The NCCN-FACT FOSI-18 and the FACT-Ntx will be collected at enrollment in conjunction with collection of patient preferences data. These instruments will elicit patient-reported outcomes that complement and supplement the preferences data. It is critical when examining preferences to have information on the current condition of those being queried.

8.0 **EVALUATION CRITERIA**

8.1 Antitumor Effect – Solid Tumors

Response and progression will be evaluated in this study using the new international criteria proposed by the revised Response Evaluation Criteria in Solid Tumors (RECIST) guideline (version 1.1) [13]. Changes in the largest diameter (unidimensional measurement) of the tumor lesions and the shortest diameter in the case of malignant lymph nodes are used in the RECIST criteria.

8.1.1 Disease Parameters

Measurable disease: Measurable lesions are defined as those that can be accurately measured in at least one dimension (longest diameter to be recorded) as ≥ 10 mm with CT scan, as ≥ 20 mm by chest x-ray, or ≥ 10 mm with calipers by clinical exam. All tumor measurements must be recorded in decimal fractions of centimeters.

Note: Tumor lesions that are situated in a previously irradiated area will not be considered measurable unless progression is documented or a biopsy is obtained to confirm persistence at least 90 days following completion of radiation therapy.

Malignant lymph nodes: To be considered pathologically enlarged and measurable, a lymph node must be ≥ 15 mm in short axis when assessed by CT scan (CT scan slice thickness recommended to be no greater than 5 mm). At baseline and in follow-up, only the short axis will be measured and followed.

Non-measurable disease: All other lesions (or sites of disease), including small lesions (longest diameter < 10 mm or pathological lymph nodes with ≥ 10 to < 15 mm short axis), are considered non-measurable disease. Leptomeningeal disease, ascites, pleural/pericardial effusions, lymphangitis cutis/pulmonitis, inflammatory breast disease, and abdominal/pelvic masses (identified by physical exam and not CT or MRI), are considered as non-measurable.

Notes:

Bone lesions: Lytic bone lesions or mixed lytic-blastic lesions, with identifiable soft tissue components, that can be evaluated by CT or MRI can be considered as measurable lesions if the soft tissue component meets the definition of measurability described above. Blastic bone lesions are non-measurable.

Cystic lesions: Cystic lesions that meet the criteria for radiographically defined simple cysts should not be considered as malignant lesions (neither measurable nor non-measurable) since they are, by definition, simple cysts. “Cystic lesions” thought to represent cystic metastases can be considered as measurable lesions, if they meet the definition of measurability described above. However, if non-cystic lesions are present in the same patient, these are preferred for selection as target lesions.

Target lesions: All measurable lesions up to a maximum of 2 lesions per organ and 5 lesions in total, representative of all involved organs, should be identified as **target lesions** and recorded and measured at baseline. Target lesions should be selected on the basis of their size (lesions with the longest diameter), be representative of all involved organs, and in addition should be those that lend themselves to reproducible, repeated measurements. It may be the case that, on occasion, the largest lesion does not lend itself to reproducible measurement, in which circumstance the next largest lesion which can be reproducibly measured should be selected. A sum of the diameters (longest for non-nodal lesions, short axis for nodal lesions) for all target lesions will be calculated and reported as the baseline sum diameters. If lymph nodes are to be included in the sum, then only the short axis is added into the sum. The baseline sum diameters will be used as reference to further characterize any objective tumor regression in the measurable dimension of the disease.

Non-target lesions: All other lesions (or sites of disease) including any measurable lesions over and above the 5 target lesions should be identified as **non-target lesions** and should also be recorded at baseline. Measurements of these lesions are not required, but the presence, absence, or in rare cases unequivocal progression of each should be noted throughout follow-up.

8.1.2 Methods for Evaluation of Disease

All measurements should be taken and recorded in metric notation using a ruler or calipers. All baseline evaluations should be performed as closely as possible to the beginning of treatment and never more than 4 weeks before the beginning of the treatment.

The same method of assessment and the same technique should be used to characterize each identified and reported lesion at baseline and during follow-up. Imaging-based evaluation is preferred to evaluation by clinical examination unless the lesion(s) being followed cannot be imaged but are assessable by clinical exam.

Clinical lesions: Clinical lesions will only be considered measurable when they are superficial (e.g. skin nodules and palpable lymph nodes) and ≥ 10 mm diameter as assessed using calipers (e.g. skin nodules). In the case of skin lesions, documentation by color photography, including a ruler to estimate the size of the lesion, is recommended.

Chest x-ray: Lesions on chest x-ray are acceptable as measurable lesions when they are clearly defined and surrounded by aerated lung. However, CT is preferable.

Conventional CT and MRI: This guideline has defined measurability of lesions on CT scan based on the assumption that CT slice thickness is 5 mm or less. If CT scans have slice thickness greater than 5 mm, the minimum size for a measurable lesion should be twice the slice thickness. MRI is also acceptable in certain situations (e.g., for body scans), but NOT lung.

Use of MRI remains a complex issue. MRI has excellent contrast, spatial, and temporal resolution; however, there are many image acquisition variables involved in MRI, which greatly impact image quality, lesion conspicuity, and measurement. Furthermore, the availability of MRI is variable globally. As with CT, if an MRI is performed, the technical specifications of the scanning sequences used should be optimized for the evaluation of the type and site of disease. Furthermore, as with CT, the modality used at follow-up should be the same as was used at baseline, and the lesions should be measured/assessed on the same pulse sequence. It is beyond the scope of the RECIST guidelines to prescribe specific MRI pulse sequence parameters for all scanners, body parts, and diseases. Ideally, subsequent image acquisitions should use the same type of scanner and follow the baseline imaging protocol as closely as possible. If possible, body scans should be performed with breath-hold scanning techniques.

PET-CT: At present, the low-dose or attenuation correction CT portion of a combined PET-CT is not always of optimal diagnostic CT quality for use with RECIST measurements. PET-CT scans are not always done with oral and IV contrast. In addition, the PET portion of the CT introduces additional data which may bias an investigator if it is not routinely or serially performed.

FDG-PET: While FDG-PET response assessments need additional study, it is sometimes reasonable to incorporate the use of FDG-PET scanning to complement CT scanning in assessment of progression (particularly possible “new” disease). New lesions on the basis of FDG-PET imaging can be identified according to the following algorithm:

- a. Negative FDG-PET at baseline, with a positive FDG-PET at follow-up is a sign of PD based on a new lesion.
- b. No FDG-PET at baseline and a positive FDG-PET at follow-up: If the positive FDG-PET at follow-up corresponds to a new site of disease confirmed by CT, this is PD. If the positive FDG-PET at follow-up is not confirmed as a new site of disease on CT, additional follow-up CT scans are needed to determine if there is truly progression occurring at that site (if so, the date of PD will be the date of the initial abnormal FDG-PET scan). If the positive FDG-PET at follow-up corresponds to a pre-existing site of disease on CT that is not progressing on the basis of the anatomic images, this is not PD.

Note: A “positive” FDG-PET scan lesion means one that is FDG avid with an uptake greater than twice that of the surrounding tissue on the attenuation corrected image.

Ultrasound: Ultrasound is not useful in assessment of lesion size and should not be used as a method of measurement. Ultrasound examinations cannot be reproduced in their entirety for independent review at a later date and, because they are operator dependent, it cannot be guaranteed that the same technique and measurements will be taken from one assessment to the next. If new lesions are identified by ultrasound in the course of the study, confirmation by CT or MRI is advised. If there is concern about radiation exposure at CT, MRI may be used instead of CT in selected instances.

Endoscopy, Laparoscopy: The utilization of these techniques for objective tumor evaluation is not advised. However, such techniques may be useful to confirm complete pathological response when biopsies are obtained or to determine relapse in trials where recurrence following complete response (CR) or surgical resection is an endpoint.

CA-125 (Ovarian, fallopian tube and primary peritoneal cancer trials): CA-125 alone cannot be used to assess response. If CA-125 is initially

above the upper normal limit, it must normalize for a patient to be considered in complete clinical response. Specific guidelines for CA-125 response (in recurrent ovarian cancer) have been published [14].

Cytology, Histology: These techniques can be used to differentiate between partial responses (PR) and complete responses (CR) in rare cases, e.g., residual lesions in tumor types, such as germ cell tumors, where known residual benign tumors can remain.

It is mandatory to obtain cytological confirmation of the neoplastic origin of any effusion that appears or worsens during treatment when measurable disease has met criteria for response or stable disease. This confirmation is necessary to differentiate response or stable disease versus progressive disease, as an effusion may be a side effect of the treatment.

8.1.3 Response Criteria

Determination of response should take into consideration all target and non-target lesions and if appropriate, biomarkers.

8.1.3.1 Evaluation of Target Lesions

Complete Response (CR): Disappearance of all target lesions. Any pathological lymph nodes (whether target or non-target) must have reduction in short axis to < 10 mm.

Partial Response (PR): At least a 30% decrease in the sum of the diameters of target lesions, taking as reference the baseline sum diameters

Progressive Disease (PD): At least a 20% increase in the sum of the diameters of target lesions, taking as reference the smallest sum on study (this includes the baseline sum if that is the smallest on study). In addition to the relative increase of 20%, the sum must also demonstrate an absolute increase of at least 5 mm. (Note: the appearance of one or more new lesions is also considered progressions).

Stable Disease (SD): Neither sufficient shrinkage to qualify for PR nor sufficient increase to qualify for PD, taking as reference the smallest sum diameters while on study.

Not evaluable (NE): When at least one target lesion is not evaluated at a particular time point.

8.1.3.2 Evaluation of Non-Target Lesions

Complete Response (CR): Disappearance of all non-target lesions. All lymph nodes must be non-pathological in size (< 10 mm short axis).

Note: If CA-125 is initially above the upper normal limit, it must normalize for a patient to be considered in complete clinical response.

Non-CR/Non-PD: Persistence of one or more non-target lesion(s)

Progressive Disease (PD): Appearance of one or more new lesions and/or *unequivocal progression* of existing non-target lesions. *Unequivocal progression* should not normally trump target lesion status. It must be representative of overall disease status change, not a single lesion increase.

Not evaluable (NE): When at least one non-target lesion is not evaluated at a particular time point.

Although a clear progression of only “non-target” lesions is exceptional, the opinion of the treating physician should prevail in such circumstances, and the progression status should be confirmed at a later time by the review panel (or Principal Investigator).

8.1.3.3 Evaluation of Biomarkers

If serum CA-125 is initially above the upper normal limit, it must normalize for a patient to be considered in complete clinical response.

8.1.3.4 Evaluation of Best Overall (unconfirmed) Response

The best overall response is the best time point response recorded from the start of the treatment until disease progression/recurrence (taking as reference for progressive disease the smallest sum recorded since baseline). The patient's best response assignment will depend on the achievement of both measurement and confirmation criteria in some circumstances.

Time Point Response for Patients with Measurable Disease at baseline (i.e., Target Disease)

Target Lesions	Non-Target Lesions	Biomarker CA-125	New Lesions*	Time Point Response
CR	CR	Within normal limits	No	CR
CR	Non-CR/Non-PD	Any value	No	PR
CR	NE	Any value	No	PR
PR	Non-PD or NE	Any value	No	PR
SD	Non-PD or NE	Any value	No	SD
NE	Non-PD	Any value	No	NE
PD	Any	Any value	Yes or No	PD
Any	PD**	Any value	Yes or No	PD
Any	Any	Any value	Yes	PD

*See RECIST 1.1 manuscript for further details on what is evidence of a new lesion

** In exceptional circumstances, unequivocal progression in non-target lesions may be accepted as disease progression.

CR = complete response, PR = partial response, SD = stable disease, PD = progressive disease, and NE = inevaluable.

8.1.3.5 Best Overall Confirmed Response

Confirmation of CR and PR for determination of best overall response is required for studies with a primary endpoint that includes response. SD should also be confirmed. **Responses (CR and PR) require confirmation at greater than or equal to 4 weeks from initial documentation. For this study, the minimum criterion for SD duration is 6-8 weeks.**

Confirmed CR and PR for best overall confirmed response

Time Point Response First time point	Time Point Response Subsequent time point	BEST overall confirmed response
CR	CR	CR
CR	PR	SD, PD or PR*
CR	SD	SD provided minimum criteria for SD duration met, otherwise, PD
CR	PD	SD provided minimum criteria for SD duration met, otherwise, PD

CR	NE	SD provided minimum criteria for SD duration met, otherwise, NE
PR	CR	PR
PR	PR	PR
PR	SD	SD
PR	PD	SD provided minimum criteria for SD duration met, otherwise, PD
PR	NE	SD provided minimum criteria for SD duration met, otherwise, NE
NE	NE	NE

*If a CR is *truly* met at first time point, then any disease seen at a subsequent time point, even disease meeting PR criteria relative to baseline, makes the disease PD at that point (since disease must have reappeared after CR). However, sometimes ‘CR’ may be claimed when subsequent scans suggest small lesions were likely still present and in fact the patient had PR or SD, not CR at the first time point. Under these circumstances, the original CR should be changed to PR or SD and the best response is PR or SD.

In non-randomized trials where response is part of the primary endpoint, confirmation of CR or PR is needed to deem either one the “best overall response.” Patients with a global deterioration of health status requiring discontinuation of treatment or who die without objective evidence of disease progression at that time should be reported to be off study treatment due to “symptomatic deterioration.” Every effort should be made to document the objective progression even after discontinuation of treatment.

8.1.4 CA125 Response Criteria

A response according to CA 125 has occurred if there is at least a 50% reduction in CA 125 levels from a pretreatment sample. The response must be confirmed and maintained for at least 28 days. Patients can be evaluated according to CA125 only if they have a pretreatment sample that is at least twice the upper limit of normal and within 2 weeks prior to starting treatment [14].

8.1.5 Duration of Response

Duration of overall response: The duration of overall response is measured from the time measurement criteria are met for CR or PR (whichever is first recorded) until the first date that recurrent or

progressive disease is objectively documented (taking as reference for progressive disease the smallest measurements recorded since the treatment started).

The duration of overall CR is measured from the time measurement criteria are first met for CR until the first date that progressive disease is objectively documented.

Duration of stable disease: Stable disease is measured from study entry (date of registration) until the criteria for progression are met, taking as reference the smallest measurements recorded since the treatment started, including the baseline measurements.

8.1.6 Progression-Free Survival

Progression-Free Survival (PFS) is defined as the duration of time from study entry to time of progression or death, whichever occurs first.

8.1.7 Survival

Survival is defined as the duration of time from study entry to time of death or the date of last contact.

9.0 DURATION OF STUDY

- 9.0 Patients will receive therapy until disease progression or intolerable toxicity intervenes. The patient can refuse the study treatment at any time.
- 9.1 All patients will be treated (with completion of all required case report forms) until disease progression or study withdrawal. Patients will then be followed (with physical exams and histories) every three months for the first two years and then every six months for the next year. Patients will be followed for OS for up to 3 years after completing the study (due to either disease progression or study withdrawal).

10.0 ADVERSE EVENTS, STUDY MONITORING & REPORTING PROCEDURE

There must be adequate review, assessment, and monitoring of adverse events. All subjects will be closely monitored throughout the study for AEs. Investigators will assess the occurrence of AEs and serious adverse events (SAEs) at all subject evaluations and visits during the study. All AEs and SAEs whether volunteered by the subject, discovered by study personnel during questioning, or detected through physical examination, laboratory test, or other means will be recorded in the subject's medical record and on the appropriate AE or SAE CRF page.

Any SAE due to any cause must be reported to the Duke Cancer Institute (DCI) Safety Desk at the Duke University by fax or email within 24-hours of learning of the event.

This study will utilize the CTCAE (NCI Common Terminology Criteria for Adverse Events), version 4.0 for Adverse Event (AE) and Serious Adverse Event (SAE) reporting. A copy of the CTCAE v4.0 can be downloaded from <http://ctep.cancer.gov/reporting/ctc.html>.

10.1 Safety

For safety information on Nintedanib, refer to the most recent version of the investigator brochure.

10.2 Reporting Period

Serious adverse events require immediate notification (within 24 hours of knowledge of the event) to [name] [name] of Duke University Medical Center or designated representative. The study period during which all AEs and SAEs must be reported begins after informed consent is obtained and initiation of study treatment on Cycle 1, Day 1. It ends 30 days following the last administration of study treatment, or if the patient initiates treatment with a new anti-cancer therapy, or study discontinuation/termination; whichever is earlier. Any SAEs occurring any time after this period should be promptly reported if a causal relationship to the investigational product is suspected; investigators should report only SAEs that are attributed to study treatment.

SAEs that are observed or reported prior to initiation of study treatment should be recorded as SAEs on the CRF if they are associated with protocol-mandated interventions (e.g., invasive procedures such as biopsies, medication washout, or no treatment run-in).

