5.3 Criteria for removal from treatment

5.3.1 Inability to tolerate Nintedanib at the lowest doses because of toxicity.

5.3.2 Patients may choose to withdraw from the study at any time for any reason.

5.3.3 Patients with evidence of disease progression or significant side effects will be removed from study.

5.3.4 Patients who become pregnant will be removed from the study.

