10.11 Procedures For Reporting

Reporting of Adverse Events:

Upon inclusion into a trial, the patient's condition is assessed (e.g., documentation of history/concomitant diagnoses and diseases), and relevant changes from baseline are noted subsequently.

All adverse events, serious and non-serious, occurring during the course of the clinical trial (i.e., from signing the informed consent onwards through the trial defined follow-up period) will be collected, documented and reported by the investigator. For each adverse event, the investigator will provide the onset date, end date, intensity, treatment required, outcome, seriousness, and action taken with the investigational drug. The investigator will determine the expectedness of the investigational drug to the AEs as defined in the Listed Adverse Events section of the Boehringer Ingelheim's Investigator Brochure for the Product.

Serious Adverse Events (SAEs) and unknown reactions or unexpected events that occur in the course of any patient's treatment on study or within 30 days following cessation of treatment should be reported to the Principal Investigator and the lead site/Sponsor ([name]/Duke University) within 24 hours of learning of the event. SAEs must be recorded using the Boehringer Ingelheim SAE Reporting Form, found in the Procedure Manual.

Additional information and/or corrections may be submitted as they are obtained. All SAEs must be followed through resolution or stabilization.

All adverse events, regardless of severity, and whether or not ascribed to the study drug administration, will be recorded in the appropriate section of the Case Report Form. Patients withdrawn from the study due to AEs will be followed by the Investigator until the outcome is determined and, when appropriate, additional written reports and documentation will be provided.

The DCI Safety Desk at Duke University should be contacted when reporting an SAE and should be faxed or emailed to the following:

DCI Safety at Duke University (on behalf of [name] [name])
[contact]
[contact]
Email: [contact]

If this person cannot be reached within 24 hours, the Principle Investigator and/or Chief Medical Officer should be contacted:

[name] [name]
Duke University Medical Center
[name]
[name]
[contact]
[contact]
[contact]

Minimum Criteria for Reporting:

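### Sections 10.2 and 10.11 set incompatible adverse event windows, and the one in 10.2 can close before 30 days after the last dose

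*Combined protocol and SAP*

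**What the plan says.** Section 10.2 defines the period for reporting all AEs and SAEs. It "begins after informed consent is obtained and initiation of study treatment on Cycle 1, Day 1". On its end, the section says: "It ends 30 days following the last administration of study treatment, or if the patient initiates treatment with a new anti-cancer therapy", then adds "or study discontinuation/termination; whichever is earlier". Two provisions reach outside that period. Before the first dose, "SAEs that are observed or reported prior to initiation of study treatment should be recorded as SAEs on the CRF", but only if they are tied to a protocol-mandated intervention. Afterwards, "Any SAEs occurring any time after this period should be promptly reported if a causal relationship to the investigational product is suspected", and investigators are told to report only SAEs attributed to treatment.

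Section 10.11 covers the same ground differently. All adverse events, serious or not, are collected "from signing the informed consent onwards through the trial defined follow-up period". SAEs arising on treatment or "within 30 days following cessation of treatment should be reported". Patients withdrawn because of an AE are followed until its outcome is known.

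Item 5.3.3 says: "Patients with evidence of disease progression or significant side effects will be removed from study". The heading of 5.3, however, refers to removal from treatment. Section 9.1 describes patients as completing the study through progression or withdrawal, and then schedules further visits for three years.

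**The concern.** Adverse event frequency and severity is objective 1.2.3, and this is a multi-center study. Two sites, each following a section of the same protocol, could report different events for identical patients, and the pooled tabulation would mix the two rules.

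The end of the window matters most. Toxicity that appears or worsens shortly after the last dose belongs in the safety profile of an oral agent given continuously. If the window closes when the patient is taken off, that interval is not systematically observed. The start date matters less, because events before the first dose cannot be nintedanib toxicity. It is still a conflict that sites have to resolve for themselves.

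**Working it through.** No figure in the plan depends on this point, so the check is a comparison of text, followed by a bound on observation time.

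**1. The windows side by side**

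| | Section 10.2 | Section 10.11 |
|---|---|---|
| Start | Cycle 1 Day 1, after consent | Signature of consent |
| Before the window | SAEs tied to protocol-mandated interventions only | Not applicable |
| End, all AEs | Earliest of: last dose + 30 days, new anti-cancer therapy, study discontinuation or termination | End of a follow-up period that is not defined |
| End, SAEs | As above, then only those attributed to treatment | 30 days after cessation, no earlier cut |

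The start dates conflict. The 10.2 end can fall before either end in 10.11. The undefined follow-up period could mean 30 days or, if it refers to 9.1, three years.

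**2. Does study discontinuation mean the patient or the trial?**

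Three things favour the patient. The other two end points in the same sentence are patient-level. Item 5.3.3 removes patients from study. Section 9.1 treats progression or withdrawal as completing the study. Two things point the other way: the heading of 5.3 refers to treatment, and 9.1 keeps seeing patients after removal. The term is not defined, so either reading is open to a site.

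**3. Who is affected under the patient-level reading?**

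Item 5.3.3 names progression alongside side effects; 5.3.2 and 5.3.4 add voluntary withdrawal and pregnancy. The design hypotheses in 11.3 put 6-month PFS at 13% (null) or 27% (alternative), so 1 − 0.27 = 73% to 1 − 0.13 = 87% of patients would progress or die within six months. Progression is therefore likely to be a common route off study.

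**4. Which events could be lost?**

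- New non-serious AEs between removal and day 30.
- SAEs in that interval judged unrelated to treatment.
- Non-serious events of special interest. Section 10.4 puts these on the SAE time line, but the provision in 10.2 for events after the window names SAEs only.

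Drug-related SAEs (10.2) and the AE that led to withdrawal (10.11) are not lost.

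**5. Does the schedule fill the gap?**

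The 7.1 table has no Toxicity Assessment under post-treatment follow-up, and note 10 leaves safety laboratory tests there to the study doctor's discretion. The toxicity form in 10.14 falls due at the start of each subsequent cycle, which never comes for a patient who has stopped. The visits in 9.1 are every three months, beyond a 30-day window. The one-month collection in note 11 of 7.1 is for research samples.

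**6. Upper bound on lost observation time**

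Assume the window closes at the last dose, so that all 30 days are lost. With T days on treatment, the share of the observation time lost is 30/(T + 30).

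| T (days) | Share lost |
|---|---|
| 28 | 30/58 = 51.7% |
| 56 | 30/86 = 34.9% |
| 116 | 30/146 = 20.5% |
| 168 | 30/198 = 15.2% |

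The 116 days is the median quoted in 2.4 for a maintenance trial at a different dose; the other values of T are assumed. The loss is smaller if dosing had already been held. A patient stopped under 6.5 after more than 21 days without drug, and removed only then, has fewer than 30 − 21 = 9 days left. These are shares of observation time. Turning them into missed events would need a post-treatment event rate, which the documents do not give.

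**The case against.** The strongest reply is that this is a wording inconsistency with safeguards around it. Section 10.2 itself keeps suspected drug-related SAEs reportable without limit of time. Section 10.11 asks for SAEs to 30 days after cessation and follows AE withdrawals to outcome. The opening of section 10 requires any SAE, whatever its cause, to be reported, and AEs to be assessed at all visits during the study. Nothing says that 10.2 overrides 10.11. Reading study discontinuation as the patient's removal also leaves the 30-day clause little to do, which favours reading it as closure of the trial.

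Much of this stands. It limits what can be lost to the events listed in the working, and only where a site applies 10.2 with the patient-level reading. It does not remove the conflict. Nothing says that 10.11 prevails either, and neither the visit table nor the toxicity form leads a site to collect these events.

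A reader might infer that the loss falls selectively on patients stopped for toxicity. The documents do not support that: 5.3.3 treats progression in the same sentence, and the AE that led to withdrawal is expressly followed up.

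**Conclusion.** The conflict between 10.2 and 10.11 is established from the text, at the start and at the end of the window. Early closure at removal is conditional. It requires the patient-level reading of study discontinuation, and a site that follows 10.2 rather than 10.11. On those assumptions up to 30 days per patient go unobserved for new non-serious events and unrelated SAEs, for most patients who stop.

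It would be tempting to conclude that adverse events are under-counted, or to quote 56 × 30 = 1,680 lost patient-days. Neither follows. The first is a risk, not a demonstrated result. The second assumes full accrual and complete loss of the 30 days in every patient, and it measures time, not events. The size of any under-count cannot be computed from the documents. The point merits an amendment because it changes which events are counted for a stated objective and is cheap to settle.

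**What to change.** - State one reporting window in both 10.2 and 10.11, running to 30 days after the last dose whether or not the patient has been removed from study.
- Delete study discontinuation or termination as a patient-level cut-off, or define it as closure of the whole trial.
- Reconcile the start date, and either define the follow-up period named in 10.11 or replace the term.
- Make 5.3.3 and its heading agree on whether removal is from treatment or from study. Add a post-treatment Toxicity Assessment to the 7.1 table, and a due date for the toxicity form that covers the interval after the last cycle.
- Tie the Secondary Aim 2 tabulation to that window.
- The cut at a new anti-cancer therapy may stay as the sponsor's choice, provided both sections state it identically.

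The cost is amendment wording and modest extra AE data entry. Event counts may rise slightly.
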